9.2.3. PGA

Physicians Global Assessment will be performed for each subject at scheduled visits to determine the SLE disease activity for each subject at the visit. The assessment is measured on a 0 to 100 Millimeter (mm) scale with score 0 to be No Disease Activity and score 100 to be the most Severe Disease Activity. The improvements from Baseline (Day 1) to Day 85 and from Baseline (Day 1) to Day 169 in PGA scores will be evaluated as part of the secondary efficacy endpoints.

Summary of observed values: Observed values and the change from baseline at each scheduled visit will be summarized. In addition to the LOCF imputation described below, the change from Baseline will be analyzed using Mixed effect Model Repeat Measurement (MMRM) method as described in the SAP Section 9.1.

Summary of imputed values: Imputed values and the change from Baseline (Day 1) in the PGA score at each scheduled visit will also be analyzed. The two-sample t-test will be used for the treatment group comparison on the change from Baseline. LOCF will be used to impute missing values on the FAS.

9.2.4. FACIT-Fatigue Scale

FACIT-Fatigue Scale assessment is a subject reported outcome. It will be performed by each subject at scheduled visits to determine the SLE disease activity for each subject at the visit. The improvements from Baseline (Day 1) to Day 85 and from Baseline (Day 1) to Day 169 in

FACIT-Fatigue assessment total scores will be evaluated as part of the secondary efficacy endpoints.

FACIT-Fatigue assessment has 13 questions and is measured with scores of 0 (Not at all), 1 (A little bit), 2 (Somewhat), 3 (Quite a bit) or 4 (Very much). All FACIT-Fatigue scales are scored so that a higher score is better. As each of the 13 items of the FACIT-Fatigue scale ranges from 0-4, the range of possible scores is 0-52, with 0 being the worst possible score and 52 the best. To obtain the 0-52 score, each negatively-worded item response is recoded so that 0 is a bad response and 4 is good response. All responses are added with equal weight to obtain the total score. In cases where some answers may be missing, a total score is prorated from the scores of answered items, as long as more than 50% of the items (i.e., at least 7 of 13) were answered.

If there are missing items, subscale scores can be prorated. This is done by multiplying the sum of the subscale by the number of items in the subscale, then dividing by the number of items actually answered. This can be done by using the formula below:

Prorated subscale score = [Sum of item scores] x [N of items in subscale] / [N of items answered]

A computer program written in SAS for the FACIT-Fatigue Scale scoring is available in Appendix I of the SAP.

Summary of observed values: Observed values of total score and the change from baseline at each scheduled visit will be summarized. In addition to the LOCF imputation described below, the change from Baseline on observed values will be analyzed using Mixed effect Model Repeat Measurement (MMRM) method as described in the SAP Section 9.1.

Summary of imputed values: Imputed values and the change from Baseline (Day 1) in the FACIT-Fatigue Scale total score at each scheduled visit will also be analyzed. The two-sample t-test will be used for the treatment group comparison on the change from Baseline. LOCF will be used to impute missing values on the FAS.

Summary of non-censored values: Non-censored values and LOCF imputed non-censored values as well as the change and percent change from Baseline (Day 1) in the FACIT-Fatigue Scale total score at Days 85 and 169 and at each scheduled visit will also be analyzed. The two-sample t-test will be used for the treatment group comparison on the change from Baseline. The following values will be censored based on blinded review before database lock:

- a. Values obtained within 60 days of a steroid (systemic/oral/topical but not ophthalmic or inhaled) dose that is increased above baseline for more than one day

- b. Addition of other systemic agents for lupus (such as antimalarials, methotrexate, rituximab, dapsone)

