### 12.3 Baseline (Day 1) Procedures

Prior to study drug administration (pre-dose procedures):

- the inclusion/exclusion criteria will be re-evaluated (CLASI score and concomitant medications only);
- directed physical examination;
- pregnancy test (urine);
- AE Assessment;
- interim medical/medication history;
- vital signs (temperature, respiratory rate, blood pressure and pulse);
- clinical laboratory evaluations (Chem-20, CBC, and UA);
- measurement of SLE disease activity (CLASI, SLEDAI-2K, BILAG-2004, PGA);
- tender and swollen joint count
- photographs of cutaneous SLE lesions;
- FACIT Index (subject completes form);
- serum sample for study drug concentration;
- serum for protein analysis;
- serum sample for measurement of RNase activity;
- whole blood for gene expression profile;
- serum sample for autoantibody profile (Ro-52/60, La, Sm, SmRNP, U1 RNP A/68, dsDNA) C3 and C4 (local or central laboratory);
- serum for assessment of antibodies to RSLV-132;
- **after completion of above assessments:**
  - study drug administration

### 12.4 Procedures on Days 8, 15, 43, 71, 99, 127, and 155

Prior to study drug administration (pre-dose procedures):

- adverse event assessment;
- interim medication history;
- vital signs (temperature, respiratory rate, blood pressure and pulse);
- serum for assessment of anti-RSLV-132 antibodies (Day 15 only)
- measurement of cutaneous disease activity (CLASI) – (Days 99, 127 and 155 only);
- **after completion of above assessments:**
  - study drug administration

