### 12.5 Procedures on Days 29, 57, 85, 113, 141, and 169/End of Treatment (EOT)

Prior to study drug administration (pre-dose procedures):

- directed physical examination;
- adverse event assessment;
- interim medication history;
- vital signs (temperature, respiratory rate, blood pressure and pulse);

- Chem-20, CBC, UA;
- measurement of SLE activity (SLEDAI-2K, BILAG-2004, PGA);
- measurement of cutaneous disease activity (CLASI);
- tender and swollen joint count;
- photographs of cutaneous disease activity (Days 85 and 169 only);
- FACIT fatigue index (subject completes form) (Days 85 and 169 only);
- serum for study drug concentration (Days 29, 85, and 169 only);
- serum for protein analysis (Day 85 and 169 only);
- serum for RNase activity (Days 29, 85, and 169 only);
- whole blood for gene expression profile (Days 29, 85, and 169 only);
- serum for autoantibody profile (Ro-52/60, La, Sm, SmRNP, U1 RNP A/68, dsDNA) C3 and C4 (local or central laboratory);
- serum for assessment of anti-RSLV-132 antibodies (Days 29 and 85 only);
- **after completion of above assessments:**
  - study drug administration (except Day 169)

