3.2.5. Missing Data and Outliers

Every attempt will be made to capture all study data. For subjects whose visit value is missing, the last observation will be carried forward (LOCF) for the efficacy analyses. Any missing, unused, or spurious data will be noted in the final CSR.

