12. SAP REVISION

Revision Date	Section	Summary of Revision	Reason for Revision
July 6, 2017	2.3.3	Updated Table 1 Study Procedures.	Protocol Amendment 4.0
	2.3.5	Updated that efforts will be made to perform all EOT and EOS assessments outlined in Protocol Appendix A.	Protocol Amendment 5.0
	6.2	Clarify the summaries.	Per sponsor request.
	6.3	Clarify to summarize the major protocol deviations.	Per sponsor request.
	7.1	Added the overall mean for prednisone or equivalent dose.	Per sponsor request.
	7.2	Clarify to summarize the Medical History Body Systems	Per sponsor request.
	9	Remove text “RSLV-132 plasma levels and RNase activity” from Efficacy Analyses.	They are not part of the efficacy analyses.
	9.2.2	No statistical testing will be performed for the imputed values of BILAG-2004 Index Assessment.	Per sponsor request.
	9.2.6	Specify to summarize at Day 169 only.	Per sponsor request.
	9.2.7	Remove text “Fisher’s exact test will be used for the treatment group comparison” under the summary of observed values.	No treatment group comparison will be made on observed values.
	9.3.1	Adding dsDNA as part of the autoantibody profile.	Protocol Amendment 4.0
		Adding a summary for the actual values.	Per sponsor request.
	10.1.2	Adding patient year calculations for the adverse event summary	Per sponsor request.

	10.2.1	Adding grade 3 or higher toxicity summaries for the safety lab data.	Per sponsor request.
	10.2.4	Replace text “Appendix B” with “Appendix A”.	Correct protocol reference.
		Physical exam results will be listed only.	Per sponsor request.
March 10, 2020	3.2.7	Revise baseline definition to consider screening.	Internal document consistency.
	6.2	Removing “plus 1” in the Total duration of infusion (Hours) calculation.	Clarification.
	9.1, 9.2.1, 9.2.3, 9.2.4 and 9.2.5	Adding repeated measurement analysis in addition to the LOCF imputation.	A less biased method by missing data compare to LOCF.
	9.1, 9.2.4, 9.2.7	Add non-censored summaries.	Per sponsor request.
	9.2.6	Include table of Predinsone Equivalent dosing.	Facilitate grouping of corticosteroids.
	10.2.4	Adding Physical Exam summary by categories of Normal/Abnormal (CS/NCS).	To be compliant with FDA ICH E3 guideline and to be consistent with Resolve RSLV-132-04 study.
	11	PK not in scope of SAP.	

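### At Day 85 the only scheduled FACIT-Fatigue value LOCF can carry is Baseline, so a missing or rescue-censored score enters the t-test as zero change unless an early EOT score is mapped there

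*SAP*

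**What the plan says.** **Schedule.** Protocol 12.3 lists the questionnaire before dosing on Day 1: "FACIT Index (subject completes form". Protocol 12.5 limits later collection: "FACIT fatigue index (subject completes form) (Days 85 and 169 only". It is not among the screening procedures (Protocol 12.2). Protocol Appendix A shows the same three time points.

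**Imputation and test.** SAP 3.2.5 sets the general rule: "For subjects whose visit value is missing, the last observation will be carried forward (LOCF) for the efficacy analyses". SAP 9.2.4 applies it to FACIT: "Imputed values and the change from Baseline (Day 1) in the FACIT-Fatigue Scale total score at each scheduled visit will also be analyzed". It repeats the rule ("LOCF will be used to impute missing values on the FAS") and adds the comparison: "The two-sample t-test will be used for the treatment group comparison on the change from Baseline". Neither section bars Baseline as the carried value.

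**Rescue censoring.** SAP 9.2.4 also analyses "Non-censored values and LOCF imputed non-censored values as well as the change and percent change from Baseline (Day 1) in the FACIT-Fatigue Scale total score", again with a t-test. Scores are censored after a qualifying steroid increase or the addition of another systemic lupus agent.

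**Other provisions.** SAP 9.2.4 plans an MMRM on observed FACIT changes. The revision log in SAP 12 gives the reason for adding it: "A less biased method by missing data compare to LOCF". Protocol 6.4 and SAP 2.3.5 ask sites to attempt the EOT assessments when treatment stops early. SAP 3.2.8 summarises by nominal CRF visit.

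**The concern.** LOCF is usually defended on the ground that the carried value is a recent on-study score. CLASI, SLEDAI-2K, PGA and the joint counts have Day 29 and Day 57 assessments that can play this role at Day 85. FACIT has none. Here the method amounts to baseline carried forward: each gap becomes a change of zero, and the t-test counts that zero as a measured outcome.

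Two things are at stake. The estimated difference mixes the drug's effect with the amount of missing data in each arm. The interval also looks narrower than the observed data justify. In the imputed non-censored analysis, a subject who needed rescue before Day 85 is entered as unchanged, and no MMRM is planned on the non-censored values. The plan keeps the LOCF t-test beside a model it calls less biased, and does not say which of the two is the FACIT comparison.

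**Working it through.** **Inputs.** From the documents: the FACIT schedule, LOCF on the FAS, a two-sample t-test, about 50 subjects randomised 2:1 (taken as 33 and 17), and two-sided 5% for information only (SAP 2.3.7). The documents give no FACIT effect, SD or missing-data rate, so there is no figure to reproduce. Those quantities are assumed below.

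**Which value can be carried to Day 85**
- Subject on treatment who misses the Day 85 form: Baseline, change 0.
- Subject whose Day 85 score is censored for rescue: Baseline, change 0.
- Subject who ends all participation before Day 85: no further data are collected (SAP 2.3.5), so Baseline, change 0.
- Subject who stops treatment before Day 85 and completes an early EOT form: that score if it is placed by date; Baseline if it is filed under nominal Day 169 (EOT). The SAP does not say which.

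With 20% of 50 subjects missing Day 85, there are 10 Baseline-carried values if none has a usable early EOT score, 5 if half do, and 0 if all do.

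**Formulas.** For an arm with mean change μ, SD σ and missing share m, with data missing completely at random and gaps set to 0:
- mean = (1 − m)μ
- variance = (1 − m)σ² + m(1 − m)μ²
- ratio of the LOCF standard error to the observed-case standard error, when the arms are alike = (1 − m)√(1 + mμ²/σ²)

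**Estimate** (assumed placebo change +3, true effect +4)
- 15% missing in both arms: 0.85 × 7 − 0.85 × 3 = 3.4, which is 15% below 4.
- 25% missing on active, 10% on placebo: 0.75 × 7 − 0.90 × 3 = 2.55, which is 36% below 4.
- No true effect, both arms improving by 5, 20% missing on active and 5% on placebo: 0.80 × 5 − 0.95 × 5 = −0.75, a false difference against the drug.

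**Standard error** (assumed μ = 5, σ = 9, so μ²/σ² = 25/81)
- m = 0.10: 0.90 × √1.0309 = 0.914
- m = 0.15: 0.85 × √1.0463 = 0.869
- m = 0.25: 0.75 × √1.0772 = 0.778

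**Test statistic with equal missingness** (placebo +3, effect +4, σ = 9, 15% missing)
- LOCF variances: 68.85 + 0.1275 × 49 = 75.10 (active) and 68.85 + 0.1275 × 9 = 70.00 (placebo). SE = √(75.10/33 + 70.00/17) = 2.53, so t = 3.4/2.53 = 1.34.
- Observed cases: SE = √(81/28.05 + 81/14.45) = 2.91, so t = 4/2.91 = 1.37.

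**Simulation** (SD units, 33 and 17 subjects, pooled t-test, 8,000 trials per case, data missing completely at random). LOCF and observed-case (OC) results:

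| Placebo change | True difference | Missing active / placebo | LOCF estimate | SE, LOCF / OC | Coverage, LOCF | Rejection, LOCF / OC |
|---|---|---|---|---|---|---|
| 0.3 | 0 | 20% / 20% | 0.00 | 0.269 / 0.334 | 95.0% | 5.0% / 5.1% |
| 0.3 | 0.5 | 10% / 10% | 0.45 | 0.287 / 0.315 | 94.7% | 32.9% / 33.6% |
| 0.3 | 0.5 | 20% / 20% | 0.40 | 0.274 / 0.334 | 93.6% | 29.3% / 31.7% |
| 0.3 | 0.5 | 30% / 30% | 0.35 | 0.260 / 0.357 | 91.8% | 24.4% / 27.1% |
| 0.3 | 0.5 | 30% / 10% | 0.29 | 0.281 / 0.330 | 87.3% | 17.1% / 31.6% |
| 0.3 | 0.5 | 10% / 30% | 0.51 | 0.267 / 0.343 | 96.1% | 43.5% / 30.1% |
| 0.5 | 0 | 30% / 10% | −0.10 | 0.278 / 0.330 | 92.3% | 7.7% / 5.2% |
| 0.5 | 0 | 10% / 30% | +0.10 | 0.269 / 0.343 | 94.2% | 5.8% / 4.9% |

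Estimates and standard errors in the table are from the formulas; coverage and rejection are simulated. With complete data the standard error would be 0.299. Every LOCF standard error in the table is below that, so replacing scores with zeros reports more precision than a trial with no missing scores.

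**The case against.** **Early EOT scores.** A reader might infer that every subject without a Day 85 score is always given a change of 0. The documents do not support that. A subject who stops treatment early may have an EOT FACIT before Day 85, and that score could be the one carried. This stands as a limit. It does not help a subject who stays on treatment and misses or is censored at Day 85, and it fails for the others too if the early score is filed under Day 169.

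**The p-value.** A reader might infer that the t-test is invalid throughout. It is not. With equal missingness the estimate and its standard error shrink almost together (t of 1.34 against 1.37), and under no true effect rejection is 5.0%. Marked distortion of the p-value needs clearly unequal missingness, which the documents neither report nor predict.

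**Size of the false difference.** The 0.75-point example is about 0.08 SD (0.75/9) and 0.29 standard errors on a 0–52 scale, and it runs against the drug. That is fair. It shows the mechanism and is no forecast.

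**Already covered.** An observed-value summary and an MMRM are planned, and the non-censored scores are also analysed without imputation. This softens the point considerably. What remains is that no analysis is named as the FACIT comparison, and the imputed t-tests stand as equals.

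**The MMRM's limits.** With two post-baseline visits, a subject missing both adds no outcome data. Fitting it to rescue-censored data assumes missing at random after rescue. Both are true, but the assumption is open to discussion, whereas a known change of zero is simply imposed.

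**Conclusion.** The point holds for the Day 85 LOCF comparisons in SAP 9.2.4, on all values and on non-censored values. It does not touch the MMRM on observed scores. With a real effect and equal missingness the estimated difference falls by the missing share. With unequal missingness, and scores that change on average, it can be too small or too large. As a measure of uncertainty about the true difference the standard error is too small: by about 9% at 10% missing and 22% at 25% missing, assuming SD 9 and mean change 5. With equal missingness and no true effect there is no bias.

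All sizes rest on assumed effects, SD and missing rates, on data missing completely at random, and on no early EOT score being used. FACIT is a secondary endpoint and p-values are descriptive (SAP 2.3.7 and 5), so the impact is moderate. It still deserves correction: in a proof-of-concept study without formal testing, the estimate and its interval are the main product.

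**What to change.** Amend SAP 9.2.4 as follows:

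- Name the planned MMRM on observed values as the between-arm comparison for FACIT-Fatigue.
- Fit the same MMRM to the non-censored values, alongside the unimputed non-censored summary already planned.
- Keep Day 85 LOCF only as a descriptive sensitivity summary labelled 'baseline carried forward', without a p-value.
- Report by arm how many values were carried from Baseline.
- State how an early EOT FACIT score is assigned to a visit.

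The cost is SAP wording and one extra model run. The price in assumptions is missing at random after rescue for the non-censored MMRM, which the SAP should state.

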9.2.5. Tender and Swollen Joint Count

Tender and swollen joint count assessment will be performed for each subject at scheduled visits to determine the SLE disease activity for each subject at the visit. Tender and swollen joint count assessment includes total of 28 joints (left and right metacarpalphalangeal joints and proximal interphalangeal joints, wrist, elbow, shoulder and knee). The total Tender and Swollen Joint Count will be summarized. The improvements from Baseline (Day 1) to Day 85 and from Baseline (Day 1) to Day 169 in tender and swollen total joint count will be evaluated as part of the secondary efficacy endpoints. Lower joint count represents less disease activity.

Summary of observed values: Observed values of total tender and swollen joint count and the change from baseline at each scheduled visit will be summarized. In addition to the LOCF imputation described below, the change from Baseline on observed values will be analyzed using Mixed effect Model Repeat Measurement (MMRM) method as described in the SAP Section 9.1.

Summary of imputed values: Imputed values and the change from Baseline (Day 1) in the tender and swollen total joint count at each scheduled visit will also be analyzed. The two-sample t-test will be used for the treatment group comparison on the change from Baseline. LOCF will be used to impute missing values on the FAS.

9.2.6. Oral Steroids Tapering

One of the objectives of the study is to evaluate the steroid sparing effects of RSLV-132. The Investigators shall decrease the use of oral corticosteroids beginning on Day 85 using the guidance stated under SAP Section 2.3.4.1. No further steroid decreases should occur from Day 141 through Day 169. The reduction in oral steroids at Day 169 relative to Day 85 will be evaluated as part of the secondary efficacy endpoints.

Summary of observed values: (1) For those who were on any oral corticosteroids at Day 85, observed of corticosteroids dose values and the change from Day 85 at Day 169 will be summarized. (2) For those who were on any oral corticosteroids with >7.5 mg/day at Day 85, observed of corticosteroids dose values and the change from Day 85 at Day 169 will be summarized.

The summary of (1) or (2) will only be performed if there are 25% or more of the subjects in the RSLV-132 group were on any oral corticosteroids at Day 85 or were on any oral corticosteroids with >7.5 mg/day at Day 85 respectively. No statistical testing will be performed.

Dose equivalence to Prednisone:

Medication	Dose Equivalence to 10 mg	Dose Equivalence to 7.5 mg
Oral Prednisone	10 mg	7.5 mg
Cortisone	50 mg	37.5 mg
Hydrocortisone	40 mg	30 mg
Methylprednisolone	8 mg	6 mg
Prednisolone	10 mg	7.5 mg
Betamethasone	1.2 mg	0.9 mg
Dexamethasone	1.5 mg	1.125 mg
Budesonide	2.25 mg	1.6875 mg
Deflazacort	12 mg	9 mg

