### 6.3 Subject Exclusion Criteria

The following will exclude potential subjects from the study:

1. severe, active CNS involvement at Screening;

2. severe renal involvement (urine protein/creatinine ratio of >200 mg/mmol, or an estimated creatinine clearance of <30 mL/min) at Screening;
3. use of cyclophosphamide within 3 months of Baseline;
4. use of background medications within 1 month of Baseline in excess of:
  - a. mycophenolate mofetil > 3 g/day;
  - b. azathioprine > 200 mg/day;
  - c. methotrexate > 25 mg/week;
  - d. hydroxychloroquine > 400 mg/day;
  - e. prednisone (or equivalent) > 15 mg/day;
5. use of an intravenous corticosteroid “pulse” within 2 months of Baseline;
6. use of an intramuscular steroid injection within 1 month of Baseline;
7. use of rituximab within 6 months of Baseline;
8. use of belimumab within 3 months of Baseline;
9. acute infection or history of acute infection within seven days prior to Baseline;
10. positive viral load test for hepatitis B, C or HIV at Screening;
11. receipt of an investigational product within 3 months of Baseline or five half-lives (whichever is longer);
12. positive pregnancy test at Screening or at Baseline;
13. female subjects currently breast feeding at Baseline;
14. inability or unwillingness to comply with study restrictions, return for follow up appointments, or other considerations, in the opinion of the Investigator, which would make the candidate unsuitable for study participation.

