### 7.3 Concomitant Medications

Subjects entering the study who had no changes to their SLE medications in the previous 30 days prior to the Baseline visit shall remain on the background medications at the same doses throughout the study. With the exception of decreases in OCS, no changes in lupus medications shall be permitted during the study, including the addition of topical steroids or topical tacrolimus, except for the rescue of a lupus flare.

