### **7.5 Treatment of Flares**

Investigators should treat lupus flares as they deem appropriate with the minimum amount of corticosteroid necessary and should return the subject to baseline steroid dose as quickly as medically reasonable. Should a subject require more than steroids for a lupus flare, investigators should treat as necessary and notify the medical monitor.

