### 11.3 Analysis of the Secondary Objectives

The following secondary objectives will be compared between the two treatment arms:

- The immunogenicity of RSLV-132 as measured by the presence of RSLV-132 antibodies
- Improvements (from Baseline to Day 85 and Day 169) in the SLEDAI-2K, PGA, and BILAG-2004 scores
- Improvement (from Baseline to Day 85 and Day 169) in the FACIT-Fatigue scale
- Improvements (from Baseline to Day 85 and Day 169) in tender or swollen joint count
- Reduction in oral steroids at Day 169 relative to Day 85
- The proportion of subjects achieving a 50% improvement in CLASI activity score

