7. BASELINE DATA

7.1. Demographic and Baseline Characteristics

Demographic (age [years], gender, race, ethnicity, height [cm], weight [kg], BMI [kg/m²]) and baseline characteristics (CLASI activity score, Number and percentage subjects with oral corticosteroids dose [Overall mean, 0 mg/day, >0 and ≤7.5 mg/day, >7.5 mg/day]) will be summarized descriptively by treatment group on the FAS. For categorical parameters, the percentages will be calculated based on the number of subjects in each treatment group of the FAS.

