9.1. Analysis of Primary Efficacy Endpoints

The primary efficacy endpoints are the improvements from Baseline (Day 1) to Day 85 and Baseline to Day 169 CLASI Activity scores.

CLASI Activity assessment will be performed for each subject at scheduled visits to determine the SLE disease activity for each subject at the visit. The assessment includes each anatomical location. The total score of the Activity subsection (defined as the sum of the scores from each anatomical location) will be used in the summary. The improvements from Baseline (Day 1) to Day 85 and from Baseline (Day 1) to Day 169 in the total activity score will be evaluated as part of the primary efficacy endpoints. Lower score represents less disease activity.

Summary of observed values: Observed values of total Activity score and the change and percent change from baseline at each scheduled visit will be summarized. In addition to the LOCF imputation described below, the primary endpoints (change from Baseline on observed values) will be analyzed using Mixed effect Model Repeat Measurement (MMRM) method. The MMRM model will include the fixed categorical effects of treatment, random effect visit, and treatment-by-visit interaction, as well as continuous fixed covariates of baseline score and baseline score-by-visit interaction. An unstructured covariance structure of random effect will be used for modeling the within-subject errors.

Summary of imputed values: LOCF imputed values and the change and percent change from Baseline (Day 1) in the CLASI Activity total score at Days 85 and 169 and at each scheduled visit will also be analyzed. The two-sample t-test will be used for the treatment group comparison on the change from Baseline.

Summary of non-censored values: Non-censored values and LOCF imputed non-censored values as well as the change and percent change from Baseline (Day 1) in the CLASI Activity total score at Days 85 and 169 and at each scheduled visit will also be analyzed. The two-sample t-test will be used for the treatment group comparison on the change from Baseline. The following values will be censored based on blinded review before database lock:

- a. Values obtained within 60 days of a steroid (systemic/oral/topical but not ophthalmic or inhaled) dose that is increased above baseline for more than one day
- b. Addition of other systemic agents for lupus (such as antimalarials, methotrexate, rituximab, dapsone)

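### SAP 9.2.6 measures steroid sparing only from the Day 85 dose, so oral flare rescue still running on Day 85 is scored as a reduction when it is stepped back towards baseline

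*SAP*

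**What the plan says.** Protocol 11.3 names the secondary endpoint: "Reduction in oral steroids at Day 169 relative to Day 85". SAP 9.2.6 puts it into practice with two descriptive summaries. Summary (1) reads: "For those who were on any oral corticosteroids at Day 85, observed of corticosteroids dose values and the change from Day 85 at Day 169". Summary (2) is the same for subjects above 7.5 mg/day at Day 85. A condition is attached: "The summary of (1) or (2) will only be performed if there are 25% or more of the subjects in the RSLV-132 group" meets the corresponding Day 85 criterion. No test is planned.

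On dosing, Protocol 7.4 asks for stable steroid doses up to Day 85 and a guided taper from then on, with no decreases from Day 141 to Day 169. Protocol 7.3 freezes lupus medication apart from oral steroid decreases, "except for the rescue of a lupus flare". Protocol 7.5 says that after treating a flare the investigator "should return the subject to baseline steroid dose as quickly as medically reasonable".

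Elsewhere the SAP does treat rescue as a problem. Sections 9.1, 9.2.4 and 9.2.7 each add a summary that censors values within 60 days of a steroid "dose that is increased above baseline for more than one day". Section 9.2.6 has no such rule.

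**The concern.** Day 85 is a sound reference for sparing only where the Day 85 dose equals the dose the subject came in on. The protocol intends this but allows one exception, flare rescue, with no time limit. When oral rescue is running on Day 85, the reference dose includes the rescue excess. Bringing the dose back down, as Protocol 7.5 directs, then produces a negative change that looks like sparing. No deviation is needed for this to happen.

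The same Day 85 dose decides who is summarised. A subject who entered on no oral steroid, or on 7.5 mg/day or less, can join summary (1) or (2) through rescue alone. In the RSLV-132 arm that subject also counts towards the 25% condition.

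What is at stake is the reading of a named secondary endpoint in a proof-of-concept study that, under SAP 5, will be interpreted by looking for trends in summaries.

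**Working it through.** The plan states no figure for this endpoint, so there is none to reproduce. The check applies the SAP rule to dose paths that the protocol permits.

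**Inputs from the documents**
- Entry cap: "prednisone (or equivalent) > 15 mg/day" is excluded (Protocol 6.3), so baseline is at most 15 mg/day.
- Taper step: 2.5 mg/day at two-week intervals from Day 85, none from Day 141 (Protocol 7.4).
- About 50 subjects, 2:1 (Protocol 5.1): 50 × 2/3 ≈ 33 on RSLV-132 and 50 × 1/3 ≈ 17 on placebo.

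**Step 1: the largest guided taper.** From 15 mg/day the steps give 12.5 (Day 85), 10 (Day 99), 7.5 (Day 113) and 5 (Day 127). The last step is at the investigator's discretion. Largest reduction: 15 - 5 = 10 mg/day.

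**Step 2: scores.** SAP score = Day 169 - Day 85. Baseline-referenced score = Day 169 - baseline. The paths are illustrative, in mg/day. The last column shows which 25% counts a subject would enter if the lower of the baseline and Day 85 doses were used.

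| Baseline / Day 85 / Day 169 | SAP score | Change from baseline | Summaries now | 25% count by lower dose |
|---|---|---|---|---|
| 10 / 20 / 10 | -10 | 0 | (1), (2) | (1), (2) |
| 5 / 15 / 5 | -10 | 0 | (1), (2) | (1) |
| 0 / 10 / 0 | -10 | 0 | (1), (2) | neither |
| 10 / 20 / 12.5 | -7.5 | +2.5 | (1), (2) | (1), (2) |
| 0 / 10 / 10 | 0 | +10 | (1), (2) | neither |
| 15 / 15 / 5 (taper) | -10 | -10 | (1), (2) | (1), (2) |
| 10 / 10 / 7.5 (taper) | -2.5 | -2.5 | (1), (2) | (1), (2) |

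In the first three rows the false reduction is exactly the Day 85 dose minus the baseline dose, and equals the maximal taper in Step 1. In the fourth row the sign reverses: the subject ends above baseline but scores as reduced. In the fifth, a subject who goes from no oral steroid to 10 mg/day scores as unchanged. Where Day 85 equals baseline, the two scores agree.

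**Step 3: the 25% condition.** 8/33 = 24.2% (not met); 9/33 = 27.3% (met). One subject on rescue can decide whether the summary appears.

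**Step 4: effect on an arm mean, under assumptions.** The documents give no flare rate, rescue dose or share on oral steroids. Assume one affected subject, a rescue excess of 5 to 20 mg/day, and roughly 25% to 75% of each arm on oral steroids at Day 85. That is 4 to 13 placebo users and 9 to 25 RSLV-132 users, 9 being the fewest that meet the 25% condition. Shift in the mean = excess / users, always towards reduction:
- Placebo: 5/13 = 0.4 to 20/4 = 5.0 mg/day.
- RSLV-132: 5/25 = 0.2 to 20/9 = 2.2 mg/day.

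One taper step is 2.5 mg/day. The upper ends pair the largest assumed excess with the fewest users.

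**The case against.** The Day 85 reference is the protocol's own endpoint and suits the design: doses are meant to be stable until Day 85, and tapering starts then. For every subject without rescue on that day, the reference is normally the baseline dose and the score is right. The affected group is narrow. Rescue must be oral, above baseline, still running on Day 85 and lower by Day 169, while Protocol 7.5 asks for the minimum dose and a quick return. Courses started and finished after Day 85 do no harm. The endpoint is untested, and the 25% condition only decides whether a descriptive table is printed. All of this stands, and it limits the weight of the point. It does not remove the mechanism, because rescue is expressly outside the stability rule.

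A reader might infer that the output could never separate a rescue step-down from a taper. The documents do not support that. Dose values are summarised with minimum and maximum (SAP 5), so a Day 85 dose above 15 mg/day in an eligible subject cannot be a baseline dose. SAP 7.1 tabulates "Number and percentage subjects with oral corticosteroids dose" in bands of zero, up to 7.5 and above 7.5 mg/day. Comparing those bands with the numbers in summaries (1) and (2) could expose paths such as 0/10/0 or 5/15/5. All data are also listed, for about 50 subjects. A path such as 10/15/10 (score 10 - 15 = -5; change from baseline 0) stays under the cap and within one band, so finding it would need the listings.

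A reader might also infer that the rule favours RSLV-132. That is not supported either: the bias flatters whichever arm has more oral rescue on Day 85. If that were placebo, it would hide a drug effect.

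**Conclusion.** The point holds as a limited weakness in a descriptive secondary endpoint. For a subject on oral rescue above baseline on Day 85, SAP 9.2.6 scores a protocol-directed step-down as steroid sparing. The false amount equals the rescue excess that has been withdrawn by Day 169. An excess of 10 mg/day matches the largest guided taper from the entry cap. Rescue alone can also bring a subject into either summary and tip the 25% condition.

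The per-subject arithmetic follows from the documents. The arm-mean range of 0.2 to 5.0 mg/day rests on the assumptions in Step 4 and on at least one such subject existing. The number affected, their split by arm and the direction of bias cannot be derived. Nothing here bears on the primary endpoint or on any error rate, and the SAP does not depart from the protocol. The case for changing it is that the remedy is cheap and uses data already collected.

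**What to change.** Change SAP 9.2.6 only:

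- Keep the Day 85 to Day 169 summary as the protocol endpoint.
- Add beside it, by arm, the change from the baseline dose to the Day 169 dose for all FAS subjects on oral corticosteroids at baseline or at Day 85. Defining the set this way keeps clear failures such as 0/10/10 in the table. Resetting membership to the baseline dose would drop them.
- Report per arm the number of subjects whose Day 85 dose is above baseline and the number whose Day 169 dose is above baseline. The first shows how far the Day 85 summary can be affected; the second shows failure to spare.
- Apply the 25% condition to the lower of the Day 85 and baseline doses, so that rescue alone cannot trigger a summary.

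Cost: one extra derivation and one extra descriptive table. The protocol endpoint is still reported as defined, and the 25% condition stands only in the SAP, so no protocol amendment is needed. No new data are needed: baseline dose is already summarised under SAP 7.1, and steroid increases above baseline are already reviewed blind before lock under SAP 9.1.
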